17.1.1 All Adverse Events

17.1.1.1 Overview of TEAEs

The overall summary of TEAEs occurring during the OLE period table will include the frequency (number and percentage) of participants with each of the following:

- Any TEAE
- IMP-Related TEAE
- Serious TEAE
- IMP-Related serious TEAE
- TEAE by intensity (NCI-CTCAE grade 1 to 4)
- IMP-Related TEAE by intensity (NCI-CTCAE grade 1 to 4)
- TEAE leading to death
- Related TEAE leading to death

Additionally, a TEAE summary table by SOC by year of OLE will be presented: number and percentage of participants by SOC for each period ([OLE W0; OLE W48],]OLE W48; OLE W96],]OLE W96; OLE W144],]OLE W144; OLE W192],]OLE W192; OLE W240],]OLE W240; OLE W288], >OLE W288).

A TEAE summary table will include a row for the overall frequency of TEAEs occurring during the OLE period of the following types:

- TEAE leading to interruption of IMP
- IMP-related TEAE leading to interruption of IMP
- TEAE leading to withdrawal of IMP
- IMP-related TEAE leading to withdrawal of IMP
- TEAE leading to concomitant medication
- IMP-related TEAE leading to concomitant medication
- TEAE leading to concomitant procedure

- IMP-related TEAE leading to concomitant procedure
- TEAE leading to study termination
- IMP-related TEAE leading to study termination

In addition, TEAE tables to be prepared are listed in Table 2 below:

Table 2: TEAE Tables to be Produced

	Overall frequency	By primary SOC and PT	By PT only	By primary SOC, PT and worst grade	OLE Period
All TEAEs	✓	~	✓	✓	~
Serious TEAEs	✓	✓	NA	NA	✓
Non-serious TEAEs*	✓	✓	NA	NA	✓
TEAEs leading to study intervention withdrawal	✓	✓	NA	NA	✓
TEAEs leading to study termination	✓	~	NA	NA	✓
TEAEs leading to death	✓	~	NA	NA	√
IMP-related TEAEs	✓	~	✓	✓	~
IMP-related serious TEAEs	✓	✓	NA	NA	✓
IMP-related TEAEs leading to treatment withdrawal	✓	✓	NA	NA	✓
IMP-related TEAE leading to study termination	✓	✓	NA	NA	√
IMP-related TEAEs leading to death	✓	✓	NA	NA	✓

^{*}A table with all TEAEs will be first provided and then only TEAEs exceeding a frequency of 5% in at least one of the treatment groups (>5%), by SOC and PT will be provided.

TEAEs will be listed by treatment group and participant during OLE.

In addition, a grouped count and percentage of participants experiencing Rash (i.e. all PTs containing Rash), a grouped count and percentage of participants experiencing Anaemia (i.e. all PTs containing Anaemia) and a grouped count and percentage of participants experiencing Leukocytosis (i.e. PTs 'Leukocytosis' and 'White blood cell count increased') will be presented for OLE period only for "Total".

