8.5 Description of Statistical Analyses

8.5.1 General Considerations

A general description of the statistical methods to be used to analyze the efficacy and safety data is outlined below. Prior to partial locking the database for the primary analysis, a detailed IAP will be developed.

Continuous variables will be summarized descriptively using the number of observations, mean, SD, median, first quartile (Q1), third quartile (Q3), minimum, and maximum. Categorical variables will be summarized using frequency counts and percentages. The denominator for the percentages will be the total number of participants in the treatment group and analysis set being presented, unless otherwise specified (e.g., on some occasions, percentages may be calculated out of the total number of participants with available data at a particular time point).

All tests of treatment effects will be conducted at a 2-sided α -level of 0.05. P-values and the 95% CIs will be presented where applicable. Actual p-values will be interpreted based on the multiple testing strategy. Treatment comparisons for each data type are described in later sections. Alternative or additional statistical methods may be used as appropriate as outlined in the IAP.

Data from all investigative sites will be pooled for all planned analyses. Analysis of individual site findings or country findings will be considered if necessary. For those measures that are analyzed using change from baseline scores, observed scores may also be presented descriptively.

The procedures to be followed in relation to handling missing, unused, or spurious data will be described in the IAP. The IAP will provide the definition(s) of Baseline measurement as required.

All participants will be included in individual participant data listings.

Any changes to the data analysis methods described in the protocol will require an amendment only if a principal feature of the protocol is affected. Any other changes to the planned data analysis that does not require a protocol amendment will be described in the IAP and the CSR.

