11.5 Presentation of continuous and qualitative variables

Continuous variables will be summarized using descriptive statistics, i.e.:

- number of participants (N)
- number and percentage of non-missing values
- number and percentage of missing values.
- mean, standard deviation (SD)
- median, 25th Percentile 75th Percentile (Q1-Q3)
- minimum, and maximum

The number of digits for non-derived and derived data, presented in outputs or available in ADaM (Analysis Data Model) datasets, is specified in the Biostatistics Outputs Assembly (BOA) document.

For both continuous and qualitative variables, percentages as 0% or 100% should be reported with the same format used for the column and together with the count of values. For example, if the count of value is zero, then display '0 (0.0)'; if the percentage is 100% then display 'xx (100.0)'.

Qualitative variables will be summarized by counts and percentages. A missing category should always be displayed at baseline – even when no missing data. A missing category, at other endpoints than baseline, should only be displayed when there are missing data.

Unless otherwise stated, the calculation of proportions will be based on the number of participants in the analysis set of interest. Therefore, counts of missing observations will be included in the denominator and presented as a separate category.

In case the analysis refers only to certain visits, percentages will be based on the number of participants in the analysis set of interest, unless otherwise specified. Total of missing and non-missing observations at each time-point will reflect the population still in the trial at that time. For example, if a participant is still in the trial at the time-point but with missing data, it should be counted in the number of missing observations.

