12.1 Disposition of Subjects and Discontinuations

A table on screened participants describing the number and percent of participants in each of following disposition categories will be produced by treatment group:

- Total number of screened subjects, i.e. subjects that gave informed consent (overall summary only)
- Number of subjects who discontinued prior to randomization and reason (overall summary only)
- Number of randomized subjects
- Number of randomized subjects who did not start treatment
- Number of randomized subjects who completed the first 24 weeks of treatment
- Number of randomized subjects who permanently discontinued treatment prior to Week 24 and reason
- Number of randomized subjects who permanently discontinued treatment after Week 24 and prior to OLE and reason
- Number of randomized subjects who completed 48 weeks of treatment
 - Number of randomized subjects who signed the OLE Informed Consent
 - Number of randomized subjects who did not sign it
- Number of randomized subjects who entered OLE at dose 75 mg QD and switched to 75 mg BID during the OLE

- Number of subjects who discontinued treatment after OLE Week 0 and prior to OLE Week 48
- Number of subjects still on treatment at OLE Week 48
- Number of subjects who discontinued treatment after OLE Week 48 and prior to OLE Week 96
- Number of subjects who completed the OLE treatment at OLE Week 96
- Number of subjects who entered a gap period at OLE Week 96
- Number of subjects still on treatment at OLE Week 96
- Number of subjects who discontinued treatment after OLE Week 96 and prior to OLE Week 144
- Number of subjects still on treatment at OLE Week 144
- Number of subjects who discontinued treatment after OLE Week 144 and prior to OLE Week
 192
- Number of subjects still on treatment at OLE Week 192
- Number of subjects who discontinued treatment after OLE Week 192 and prior to OLE Week 240
- Number of subjects still on treatment at OLE Week 240
- Number of subjects who discontinued treatment after OLE Week 240 and prior to OLE Week 288
- Number of subjects still on treatment at OLE Week 288
- Number of subjects who discontinued treatment after OLE Week 288 and prior to OLE Week 336
- Number of subjects still on treatment at OLE Week 336

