16.4 Expanded Disability Status Scale (EDSS)

Descriptive statistics for the EDSS score and EDSS CFB at each visit during the DBP and the OLE period combined will be provided by treatment group and overall on the mITT analysis set.

In addition, descriptive statistics for the EDSS score and EDSS CFB at each visit during the OLE period only will be provided by treatment group and overall on the mITT-OLE analysis set (early treatment discontinuers during OLE will be presented at 'EOT' visit).

Descriptive statistics for categorical EDSS CFB, i.e., number and proportion improving, stable, or worsening, will also be reported for each time point. Here improvement is defined as a decrease of 1.0 point or more, stable condition as a change of no more than half a point in either direction and worsening as an increase of 1.0 point or more.

Mean CFB in EDSS will be presented on mITT analysis set as a by-year line plot during DBP and OLE period combined. The plot will be provided for each treatment group and overall, with a vertical line segment at each visit representing \pm SE (jittered if needed for legibility), and with all treatment groups included in a single figure.

Additionally, the plot of mean CFB in EDSS will be presented for OLE period only (OLE Week 48 to OLE Week 336 and EOT) on mITT-OLE analysis set.

A listing will be provided for EDSS data, by participant and by timepoint for the DBP and OLE treatment period combined.

17 Safety Evaluation

The subsections in this section include specifications for summarizing safety endpoints that are common across clinical trials such as adverse events, laboratory tests and vital signs.

All outputs will be provided on the OLE period if not otherwise indicated.

Safety analyses will be based on the SAF for summaries on the DBP + OLE period and on the SAF-OLE for summaries on the OLE period, according to the as-treated principle.

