17.1.1.2 EAIR of TEAEs

EAIR of TEAEs are calculated as the number of participants with TEAE divided by the sum of the individual times of all participants in the treatment group from start of treatment to first onset of TEAE in the corresponding time period. The incidence rate multiplied with 100 would give the number of AEs expected in 100 participants within 1 time unit (year). EAIR of TEAEs will be presented by SOC and PT. Confidence interval of incidence rate will be calculated using the GENMOD procedure from SAS ® with Ismeans instruction using a Poisson binomial model. If a participant has multiple events, the exposure period of the first event will be used. For a participant with no event, the exposure period will be censored at the last follow-up time within the AE summarization period.

The EAIR of TEAE tables to be prepared are listed in Table 3 below:

Table 3: EAIR of TEAE Tables to be Produced

	Overall frequency	By primary SOC and PT	By primary SOC, PT and worse grade	OLE Period	OLE Period by year
TEAEs	Χ	Χ	X	X	Χ
IMP-related TEAEs	X	Χ	NA	X	NA
Serious TEAEs	X	Χ	NA	X	NA
IMP-related Serious TEAEs	Χ	Χ	NA	Χ	NA
TEAEs of Special Interest	×	NA (by AESI category, CMQ/SMQ and PT)	NA	X	NA

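### SAP 17.1.1.1 names no denominator for the yearly OLE TEAE percentages, so the SAP 11.5 default keeps participants who have left in every later year and a constant risk prints as a falling percentage

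*SAP*

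**What the plan says.** SAP 17.1.1.1 plans a TEAE summary by SOC and OLE year: the "number and percentage of participants by SOC for each period". There are six 48-week periods up to OLE Week 288 and a seventh for everything after it. No denominator is named.

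SAP 11.5 supplies the general rule: "Unless otherwise stated, the calculation of proportions will be based on the number of participants in the analysis set of interest". It repeats the rule for analyses restricted in time: "In case the analysis refers only to certain visits, percentages will be based on the number of participants in the analysis set of interest". Protocol 8.5.1 has the same default: "The denominator for the percentages will be the total number of participants in the treatment group and analysis set being presented, unless otherwise specified".

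The SAP 17 introduction bases safety analyses "on the SAF-OLE for summaries on the OLE period, according to the as-treated principle". Under SAP 10.2, membership of SAF-OLE requires one evobrutinib dose in the OLE, so it never shrinks.

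Four other provisions matter:
- SAP 17.1.1.2 and its Table 3 plan an exposure-adjusted incidence rate (EAIR) of TEAEs by OLE year.
- SAP 12.1 plans counts of participants still on treatment at each 48-week mark, for example "Number of subjects still on treatment at OLE Week 288".
- SAP 11.12 assigns Safety Follow-up data, in analyses by time period, to the period in which the participant discontinued.
- SAP 17.1 counts AEs that start in the Week 96 treatment gap as OLE TEAEs.

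**The concern.** Someone who stops in OLE year 1 cannot contribute a TEAE to OLE year 6, but the default rule keeps that person in the year-6 denominator. The printed percentage is then the risk among those still present multiplied by the fraction still present. As that fraction falls, so does the percentage, even if the risk is unchanged.

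Long-term safety is part of the OLE objective, and this is the planned table of TEAE percentages year by year. An apparent decline in adverse events with longer treatment is a reassuring message, and here it could come wholly from attrition. A reader would have to go to the EAIR or disposition tables to separate the two.

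**Working it through.** **Which denominator applies.** Section 17.1.1.1 is silent, section 11.5 then defaults to the analysis-set N, and section 17 makes that set SAF-OLE. One sentence in 11.5 refers to the population still in the trial, but it governs the total of missing and non-missing observations at a time-point. An AE table by period has no missing observations to count. Where the SAP wants another base it says so: in 17.4, vital signs at each time point are presented for participants who have reached it.

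**Inputs.**
- From the plan: OLE periods of 48 weeks (SAP 17.1.1.1); a year of 365.25 days (SAP 11.8), which is 365.25/7 = 52.18 weeks; an expected OLE size of about 200 (Protocol 8.1).
- Reproducing the OLE size: 0.80 × 250 = 200, as stated.
- Assumed, because the documents give no OLE values: a constant 20% risk of a TEAE per 48-week period; dropout of 5%, 12% or 15% per year, spread evenly. The 12% is the protocol's planning figure for the main study; its use in the OLE is an assumption.

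The plan states no figure for the yearly percentages, so there is none to reproduce.

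**Formulas, per 48-week period.**
- Event hazard: L = −ln(0.80) = 0.2231.
- Dropout hazard: D = −ln(1 − d) × 48/52.18.
- Share remaining at Week 240 (start of period 6): S = exp(−5D).
- Percentage among those present at the period start: P = L/(L + D) × [1 − exp(−(L + D))].
- Percentage printed with the fixed SAF-OLE N: S × P.

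**Results for period 6 (Weeks 240 to 288).**

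| Dropout per year | D | Share remaining, S | Fixed N, S × P | Period-start N, P |
|---|---|---|---|---|
| 5% | 0.0472 | 79% | 15.4% | 19.6% |
| 12% | 0.1176 | 56% | 10.5% | 18.9% |
| 15% | 0.1495 | 47% | 8.8% | 18.6% |

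In participants, at 12% dropout: 200 × 0.555 = 111 enter period 6 and about 21.0 have an event. The fixed N gives 21.0/200 = 10.5%; the period-start N gives 21.0/111 = 18.9%.

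Across periods 1 to 6 at 12% dropout, the fixed-N column reads 18.9, 16.8, 14.9, 13.3, 11.8 and 10.5%. The period-start column reads 18.9% throughout. It stays below 20% because people who leave during a period are seen for only part of it.

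**Person-time check.** With time counted only within each period, the rate is 0.2231/(48/52.18) = 24.3 per 100 participant-years in every period, whatever the dropout. A by-year EAIR built that way shows the constant risk correctly.

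**The case against.** The strongest reply is that the plan already contains the remedy. The by-year EAIR covers the same events with exposure adjustment, and section 12.1 gives the numbers on treatment at each 48-week mark. This stands, and it confines the problem to one descriptive table. It does not make that table's percentages right.

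A second reply is that Protocol 8.5.1 allows percentages out of participants with available data at a time point. It does, as an example of an exception to be specified. Neither 17.1.1.1 nor 11.5 specifies it for this table.

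Four stronger readings are tempting, and the documents do not support them:
- *That the by-year EAIR is itself wrong.* Its clock runs "from start of treatment to first onset of TEAE in the corresponding time period", which could be read as starting at the first OLE dose and would greatly dilute late-year rates. But the reference to the corresponding time period, and the rule "For a participant with no event, the exposure period will be censored at the last follow-up time within the AE summarization period", favour time bounded by the period. The wording merits one clarifying sentence and no more.
- *That the last column covers less than 48 weeks.* The only dates available are a planned first-participant quarter and the SAP version date; neither is a cut-off or last-visit date. The documents show only that the column is open-ended.
- *That nothing in the printed table would reveal the attrition.* No table shell is in the documents, so this cannot be checked.
- *That OLE percentages will in fact be roughly halved.* That rests on assumed dropout and incidence.

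**Conclusion.** The point holds as a minor one. By its own stated default, the SAP divides each OLE-year count by the full SAF-OLE N, so any attrition lowers the later percentages when the risk is constant. This is a rule with a misleading result, not merely an unstated detail.

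Only the direction comes from the documents. The illustrated gap in period 6 (about 4, 8 or 10 percentage points at 5%, 12% or 15% yearly dropout) rests on an assumed constant 20% risk per period and evenly spread dropout. It does not follow that the OLE safety evaluation as a whole is compromised: the other exposure-based and disposition summaries remain available.

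**What to change.** In SAP 17.1.1.1, define the denominator of each OLE-year percentage, per treatment group and in Total, as the SAF-OLE participants who have not permanently discontinued OLE treatment before the start of that period.
- Include participants in the Week 96 treatment gap who have not discontinued, because 17.1 counts their AEs as OLE TEAEs.
- Exclude those who are only in Safety Follow-up, because 11.12 places their data in the period of discontinuation.
- Print this N in each column header.
- Add a footnote that discontinuation or study termination within a period still lowers the percentage, that the column after OLE Week 288 is open-ended and not comparable in length with the 48-week columns, and that the by-year EAIR should be read alongside.

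In SAP 17.1.1.2, state that for the by-year EAIR the time at risk starts at the beginning of each OLE year and counts only person-time within that year.

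The cost is a few sentences, one N per column and a footnote; no new data or model is needed. Late denominators per treatment group will be small, so late percentages will be less stable, and they will look less favourable than under the default.

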17.1.1.2 EAIR of TEAEs

EAIR of TEAEs are calculated as the number of participants with TEAE divided by the sum of the individual times of all participants in the treatment group from start of treatment to first onset of TEAE in the corresponding time period. The incidence rate multiplied with 100 would give the number of AEs expected in 100 participants within 1 time unit (year). EAIR of TEAEs will be presented by SOC and PT. Confidence interval of incidence rate will be calculated using the GENMOD procedure from SAS ® with Ismeans instruction using a Poisson binomial model. If a participant has multiple events, the exposure period of the first event will be used. For a participant with no event, the exposure period will be censored at the last follow-up time within the AE summarization period.

The EAIR of TEAE tables to be prepared are listed in Table 3 below:

Table 3: EAIR of TEAE Tables to be Produced

	Overall frequency	By primary SOC and PT	By primary SOC, PT and worse grade	OLE Period	OLE Period by year
TEAEs	Χ	Χ	X	X	Χ
IMP-related TEAEs	X	Χ	NA	X	NA
Serious TEAEs	X	Χ	NA	X	NA
IMP-related Serious TEAEs	Χ	Χ	NA	Χ	NA
TEAEs of Special Interest	×	NA (by AESI category, CMQ/SMQ and PT)	NA	X	NA

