8.1 Sample Size

A per-group sample size of 44 evaluable participants provides 85% power to detect a decrease of 90% in the total number of gadolinium-enhancing T1 lesions, summed over scans at Week 12, 16, 20, and 24, between each M2951 group versus placebo at the 2-sided 5% level, using the Wilcoxon rank-sum test, where the p-value is evaluated using a continuity-corrected normal approximation to the test statistic. Power was evaluated via simulation in R of the Wilcoxon test (wilcox.test) applied to lesion count data generated according to a NB distribution, with mean $\lambda_t = 0.55$ and shape parameter $\Upsilon_t = 14.0$ for a given M2951 group (Υ_t based on rituximab data) (2), and mean $\lambda_c = 5.5$ and shape parameter $\Upsilon_c = 7.256$ for the placebo group (λ_c and Υ_c based on placebo data) (2), yielding a lesion rate ratio of $\lambda_t/\lambda_c = 0.10$. Approximately 50 participants will be randomized per group to protect against a loss of information due to a 12% drop-out rate over 1 year, and to provide for an adequate assessment of safety. (Note that the NB distribution parameterization assumed here implies lesion count variance equals $\lambda + \lambda^2 \Upsilon$ for a given treatment group.)

Approximately 250 participants will enter the main study. Assuming an 80% rate of continuation to OLE, approximately 200 participants are expected to enter the OLE Period.

FWER at the primary analysis will be controlled at the 2-sided 0.05 significance level for the 3 comparisons of M2951 dose group versus placebo using the Hochberg procedure.

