11.1 Treatment groups and Investigational Medical Product (IMP)

Treatment groups are defined according to initial actual treatment received as placebo, Evobrutinib 25 mg QD, Evobrutinib 75 mg QD, Evobrutinib 75 mg BID, and Tecfidera. All participants who choose to continue the OLE period entered on the 75 mg once daily dose and have switched to the 75 mg twice daily dose following protocol amendment V5 dated 21 November 2018. Unless otherwise indicated, all analyses will be presented separately for the 5 initial treatment groups plus combined across treatment groups (i.e., "Total"). The IMP during the OLE phase is Evobrutinib.

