11.9 Handling of missing data

Unless otherwise specified, missing data will not be replaced.

In all participant data listings, imputed values will be presented and flagged. Partial dates, which are not to be imputed according to this IAP, will be presented using the format "____YYYY".

Missing statistics, eg, when they cannot be calculated, should be presented as 'nd', with 'nd' standing for 'not done'. For example, if n = 1, the measure of variability (SD) cannot be computed and should be presented as 'nd'.

In case of zero records available for presentation in a given TLF, then an empty output with 0 occurrence or a sentence stating that there are no data will be provided. For tables of Adverse Events and Deaths (outputs required for EudraCT and/or clinicaltrial.gov), if there is no observation, the output must contain the first line 'Participant with...' or 'Participant who died' displayed with 0 occurrence.

If a System Organ Class (SOC) or Anatomical Therapeutic Class (ATC) term is missing/not coded yet, then 'Uncoded SOC' (or 'Uncoded ATC') will be indicated at the TLF level. When a Preferred Term (PT) is missing, it will be set to 'Uncoded PT:' TEAE verbatim text.

Incomplete AE-related dates will be handled as follows:

- In case the onset date is missing completely or missing partially but the onset month and year, or the onset year, are equal to the start of IMP, then the onset date will be replaced by the minimum of the start of IMP date and the AE resolution date (if not missing).
- In all other cases the missing onset day or missing onset month will be replaced by 1.
- Incomplete stop dates will be replaced by the last day of the month (if day is missing only), if not resulting in a date later than the date of participant death. In the latter case, the date of death will be used to impute the incomplete stop date.

Participants with study termination e-CRF form completed and treatment termination form missing at the time of the end of study will be handled as follows:

End of treatment status will be set to "Discontinued" and the following end of treatment information will be carried over from the study termination e-CRF form:

- Reason for discontinuation of treatment will be replaced by the reason for study discontinuation
- Reason for discontinuation of treatment protocol non-compliance/withdrawal of consent/Other, specify free-text fields will be replaced by the corresponding free-text fields in the study termination form

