17.7 Pregnancy Test

Results of pregnancy test (urine or serum) will be listed for OLE period based on SAF-OLE.

Analyses will be performed for the DBP+OLE period based on the SAF analysis set and for OLE period based on the SAF-OLE.

Data on immunoglobulin (Ig) levels, and CCl (see list of parameters in Appendix 19.2) will be summarized for the OLE period for observed values, change from OLE baseline values, and percent change from OLE baseline by treatment group and overall using descriptive statistics.

In addition, number and percent of subjects falling above, below, and within normal range will be summarized where applicable. Assessments made at the End of Treatment visit for treatment discontinuers will be windowed appropriately. Assessments made at the End of Trial visit for study discontinuers will be summarized separately from assessments made at Safety follow-up visit at OLE Week 388 End of Trial visit for study completers.

Additionally, descriptive statistics of absolute values of CCI will be provided for subjects falling above, below, and within normal range of the specific laboratory parameter. Summaries will be provided on OLE period for observed values, change from OLE baseline values, and percent change from OLE baseline by treatment group and overall.

Shift tables from OLE baseline value (low, normal, high) to end of OLE Period will be presented by treatment group and overall, for each Ig class and subclass, and parameters where applicable (see list of parameters in Appendix 19.2), using SAF-OLE analysis set.

[figure not shown]
Boxplots for each Ig class and subclass, (g/L), and CC (see list of parameters in Appendix 19.2) by treatment group and time point will be provided, for OLE period.

Line plots of median percent change from baseline will be provided by time point and treatment group on DBP and OLE combined periods for each Ig class and subclass, and (see list of parameters in Appendix 19.2).

(see list of parameters in Appendix 19.2) and Ig class and subclass levels will be listed by treatment group, participant and time point (where applicable). IgG values < 3 g/L (severe hypogammaglobulinemia) and IgG values < 6 g/L (hypogammaglobulinemia) will be flagged in the listing.

EAIR of infections

For definition of severe infections AESI, see Section 17.2.3 and Appendix 19.5.

Confidence interval of incidence rate will be calculated using the Garwood method for Poisson mean.

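### The EAIR confidence intervals are specified by a misnamed model that gives no usable upper limit for an arm with zero events; the exact Garwood interval already in the SAP should replace it

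*SAP*

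**What the plan says.** SAP 17.1.1.2 defines the EAIR as the "number of participants with TEAE divided by the sum of the individual times of all participants in the treatment group", where each participant's time runs to first onset or is censored at the last follow-up. It then takes the confidence interval from GENMOD with the LS-means "instruction using a Poisson binomial model". The section gives no link function, offset, confidence level or rule for zero events.

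The tables are fine-grained: "EAIR of TEAEs will be presented by SOC and PT". Table 3 adds worst grade and OLE year for TEAEs, and includes AESIs. SAP 11.1 sets the columns: "all analyses will be presented separately for the 5 initial treatment groups plus combined across treatment groups".

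The same SAP uses a different method for infection rates. Under the sub-heading on EAIR of infections it says: "Confidence interval of incidence rate will be calculated using the Garwood method for Poisson mean". It points to the AESI section for the events: "For definition of severe infections AESI, see Section 17.2.3 and Appendix 19.5". This text belongs to Section 17.8, the immunoglobulin section in the table of contents. In the public copy that heading is lost, so the text appears after 17.7 Pregnancy Test.

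The only text on statistics that fail to compute is SAP 11.9: "Missing statistics, eg, when they cannot be calculated, should be presented as" *nd*.

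**The concern.** The Poisson-binomial distribution describes a sum of Bernoulli trials with unequal probabilities. It is not a rate model with a person-time denominator. Poisson or negative binomial regression may have been meant, and two programmers could implement the sentence differently.

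Settling the name does not solve the main problem. GENMOD LS-means limits are Wald limits on the link scale. For an arm with no events the estimate on that scale goes to minus infinity and its standard error grows without bound, so there is no usable upper limit.

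In a long-term safety extension, the informative figure for a rare event is often how high the rate could still be when few or no events were seen. The planned method cannot give that by arm.

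**Working it through.** **Reference figure.** Neither document states an EAIR or an EAIR interval, so there is nothing of the plan's own to reproduce. The check compares the two methods on assumed data.

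**Inputs**
- Participants: Protocol 8.1 says "Assuming an 80% rate of continuation to OLE, approximately 200 participants are expected to enter the OLE Period". An even split over five groups gives 200 / 5 = 40 per arm (assumption).
- Person-time per arm: 40 × 5 years = 200 PY (assumption), varied from 120 to 240 PY. One OLE year at 365.25 days per year (SAP 11.8), with no dropout: 40 × 48 × 7 / 365.25 = 36.8 PY. The ceiling at 384 weeks is 294.4 PY.
- Level: two-sided 95%, from Protocol 8.5.1; SAP 17.1.1.2 states none.

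**Formulas**, for *d* participants with the event and *T* PY
- Model (log link, log-time offset, arm as factor): (d/T) × exp(±1.96/√d).
- Garwood: lower limit χ²(0.025; 2d)/(2T), taken as 0 when d = 0; upper limit χ²(0.975; 2d+2)/(2T). For d = 0 the upper limit is −ln(0.025)/T = 3.689/T.

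**Zero-event arm under the planned method.** A log-link Poisson model was fitted to five arms of 36.8 PY, one with no events. The table shows that arm.

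| Iterations | Log-rate estimate | SE | Upper limit per 100 PY |
|---|---|---|---|
| 5 | −8.5 | 7.0 | about 20,000 |
| 10 | −13.5 | 85.8 | 1.6 × 10⁶⁹ |
| 20 | −23.5 | 12,738 | infinite |

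The limit reflects only where the iteration stops. At 200 PY the pattern is the same. After 20 iterations a negative binomial fit gives −23.5 (SE 12,738) and a binomial logit fit −21.6 (SE 4,622), so the failure does not depend on how the name is read. The fits were run in Python. The value SAS prints will depend on its convergence criterion, but the divergence will not.

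**Limits per 100 PY at 200 PY per arm**

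| Events | Model | Garwood |
|---|---|---|
| 0 | 0 to infinity | 0 to 1.84 |
| 1 | 0.07 to 3.55 | 0.01 to 2.79 |
| 2 | 0.25 to 4.00 | 0.12 to 3.61 |
| 5 | 1.04 to 6.01 | 0.81 to 5.83 |
| 10 | 2.69 to 9.29 | 2.40 to 9.20 |

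With one or two events both model limits lie above the exact ones. The zero-event Garwood upper limit at other exposures is 3.689/120 = 3.07, 3.689/240 = 1.54, 3.689/294.4 = 1.25 and, for a single OLE year, 3.689/36.8 = 10.0 per 100 PY.

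**How often an arm is empty.** Four or fewer affected participants cannot fill five arms. If *n* affected participants fall evenly at random over five arms, the chance of at least one empty arm is 5(0.8)ⁿ − 10(0.6)ⁿ + 10(0.4)ⁿ − 5(0.2)ⁿ. This gives 96% for n = 5 (5 × 0.8⁵ = 1.6 empty arms on average), 48% for n = 10 and 6% for n = 20. In a single OLE year, a term with a true rate of 1 per 100 PY has no events in a given arm with probability exp(−0.368) = 69%.

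**Overlap with 17.8.** SAP 17.2.3 counts serious or Grade ≥ 3 infections and opportunistic infections as AESIs. Table 3 puts AESI rates under GENMOD, while 17.8 puts infection rates under Garwood. If the same infection rate is reported under both for the same group and period, its limits will differ.

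**The case against.** The best counter-argument is that the empty cells are not the main safety evidence. In the OLE every arm takes evobrutinib, first 75 mg once daily and then 75 mg twice daily, so the five columns are former double-blind groups rather than competing regimens. The Total column has a finite interval whenever any arm has an event. At one event and an assumed 1,000 PY in Total, the upper limits are 0.71 (model) and 0.56 (Garwood) per 100 PY. That lowers the weight of the point. It does not fill the arm-level cells that SAP 11.1 requires, and in the by-year tables Total can itself be zero for a term that occurred in another year.

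Second, SAP 11.9 would print *nd* in such a cell. That is a declared convention, but it supplies no limit, although one is easily computed.

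Third, 17.8 is partly blacked out, so a clash between two intervals for the same rate is possible rather than shown. That stands. The case for the change does not rest on it.

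Fourth, a narrower repair exists: name the model, link, offset and level, and use Garwood only when d = 0. That would work, but it mixes two methods within one table. A likelihood-ratio interval would also be finite at zero events (upper limit 1.92/T), but the SAP asks for LS-means.

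Fifth, Garwood is conservative: its coverage is about 97.5% to 98.8% for expected counts from 0.5 to 10, where the log-scale Wald interval ranges from about 91% to 98%. It also treats person-time as fixed, although time here stops at first onset. Both are real and minor, and 17.8 already accepts them.

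**Conclusion.** The concern holds. The model named in SAP 17.1.1.2 is not a model for person-time rates, and on any plausible reading the specified LS-means give no usable upper limit for an arm without events. Such arms are certain for terms affecting up to four participants in Total and very likely at five. For one or two events the model limits are shifted upward, and from about ten events the choice hardly matters.

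The consequence is limited to descriptive safety intervals. The failure at zero events does not depend on the assumed exposure. The sizes of the Garwood limits do: they rest on an even split of about 200 participants and on assumed follow-up, and the 36.8 PY figure is a best case for later years because it ignores dropout. The change should be made, but it does not threaten the trial's conclusions.

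**What to change.** In SAP 17.1.1.2, replace the GENMOD sentence with:

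> The two-sided 95% confidence interval of the incidence rate will be calculated with the exact Garwood method for a Poisson mean (lower limit 0 when there are no events), for all EAIR tables including AESI.

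The denominator stays as the section already defines it. This settles the model name, the missing confidence level, the zero-event cells and the difference from 17.8 together.

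The cost is one sentence and simpler programming, with slightly wider coverage than nominal as the downside. The documents do not show whether the earlier interim EAIR tables used GENMOD; if they did, a footnote on the change of method is needed.
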